Investigational Device Description	
Device Name: MedRhythm's MR-Stride Plus
 
The following materials will be provided:
 
 1. Access to Stride Plus patient application. 2. Mobile Devices. 3. Motion Sensors. 4. Headphones. 
The MedRhythms MR-Stride Plus includes a patient application and sensors with commercially available headphones and smartphones. The MR-Stride Plus is a device intended to improve gait metrics and improve walking speed. This technology uses embedded audio cues to facilitate improvements in walking speed based on Rhythmic Auditory Stimulation. When using the system, patients walk with sensors that are attached to their shoes and collect gait parameters, including the following measurements: speed, stride length, symmetry (temporal and spatial), and cadence. The algorithm uses data from the sensors to inform changes made to the audio cues. These cues, which are embedded in time-shifted music, are delivered back to the users who aim to walk to the beat.
 
Research shows that walking to an external rhythmic stimulus globally engages the brain, coupling the auditory and motor regions. For stroke survivors with damage to the motor system, this dual engagement has the effect of establishing new neural connections to the motor region. Furthermore, this has the potential to make walking certain distances, which may ordinarily be onerous or impossible tasks, achievable for these individuals. As a result of neuroplasticity, repeating these audio-cueing exercises on a consistent basis can change one's brain composition, allowing walking improvements made with the device to manifest without the engagement of the intervention.

Enrollment and Consent	Study Participants will be enrolled into the study by a study staff member at participating study sites. Once informed consent is received, Study Participants will be screened for enrollment into the study.
Study Objectives	The purpose of this clinical study is to evaluate the effects of the Stride-Plus on tolerability, biomechanics and walking speed in the acute stroke care setting in addition to its impact on length of stay. The study will also look at the impacts of the intervention on falls and cost of care over a 90-day period post-discharge from acute care setting.
Study Design	
This study will be a single site, prospective, randomized controlled clinical study. Approximately 40 individuals will be enrolled per the inclusion/exclusion criteria. Participants will be randomized using simple randomization into one of two arms. It is expected that study participants will be approximately equally distributed to either arm (20/20).
 
All interested, potential study participants will participate in the screening study phase. A member of the study team will seek informed consent and review inclusion and exclusion criteria to determine eligibility.
 
Individuals who qualify for enrollment will be randomized into one of two arms:
 
Arm A: Standard of Care + MR-Stride Plus Intervention Arm B: Standard of Care

	
For all Study Participants, standard of care will be followed in both the acute care setting and in the discharge setting. Data required to evaluate the study objectives will be collected from record review and participant interviews. Participants will not be required to physically visit the study facility for study-specific procedures once they have been discharged from the acute care setting. Participants will be contacted by telephone to answer study assessment questions (e.g., mRS) intended at Days 45 (+/-2 Days), and 90 (+/-7 Days).
 
For those Study Participants enrolled into Arm A, study staff will review the intended walking intervention therapy schedule with the study participant. The Stride Plus is intended to be used for thirty (30) minutes a day, three (3) times a week. Participants will complete the following intervention phases related to use of the Stride Plus:
 
Intervention Phase 1 (within 24 hours from admission): In addition to standard of care therapy, study participants will complete at least one (1) walking therapy session with the Stride Plus while an inpatient in the acute care setting. Additional study therapy sessions will continue until the Study Participant is discharged from the acute care setting.
 
Intervention Phase 2 (Day 1 post-discharge to Day 90): In addition to standard of care therapy, study participants will complete a series of three (3) remote walking therapy sessions a week with the Stride Plus following discharge from acute care setting. Participants will schedule their sessions according to their preference and needs. Intervention Phase 2 will continue until the Study Participant is 90 days since discharge or earlier if the study participant is withdrawn from the study therapy. Participants will complete a walking test using the Stride Plus at discontinuation to determine the walking speed.
 
Post-Intervention Phase: Participants will be followed from discontinuation of the Stride Plus until Day 90. At Day 90 (+7 days), participants will complete a walking test using the Stride Plus to determine walking speed.
 
For those study participants in Arm B, the control group, only standard of care therapy will be provided. Participants will complete a 6-meter walk test (approximately 20 feet) to measure gait speed at baseline, biweekly post- discharge from acute care to day 90 (+/-7 days) following discharge.

Primary Endpoint	
The primary study objectives are as follow:
 
 1) Change in gait speed (m/s) from baseline to study completion (90 days following discharge from acute care or earlier if study participant withdraws); 2) time-to-functional change in gait speed from baseline to study completion 3) adherence to the MR-Stride Plus therapy schedule.
Secondary Endpoint	
The secondary study objective is to assess the median length of stay in acute stroke hospital and the percent of readmission during the 90 (+/-7) days following discharge.

Participant Population	
No age, race, education or geographical restrictions apply. All individuals who meet the inclusion/exclusion criteria at participating study sites will be considered.

Inclusion Criteria	
To be enrolled and randomized into the study, potential Study Participants must meet all of the following inclusion criteria:
 
 1.0 Must be 18 years of age or older. 2.0 Must be able to read and speak English fluently. 3.0 Be within 24 hours from admission for confirmed stroke event.

	
4.0 Currently able to walk at a speed greater or equal to 0.4m/s, but less than 1.0m/s, as determined by a 6-meter walk test (approximately 20 feet) for comfortable walking speed (the average of three trials).
 
5.0 Demonstrates some level of asymmetry in gait.
 
6.0 Is expected to be discharged from the acute care setting requiring physical therapy per standard of care and participant has verbally committed to receiving at least one therapy session.
 
7.0 Able and willing to consent with proposed study schema (verbal commitment), including consent to participate in communication with the treating clinician (as needed) during the study period.
 
8.0 Score ≤1 on question 1b and a 0 on question 1c on the NIH Stroke Scale.
 
9.0 Able to safely participate in protocol-defined walking therapy sessions of 30-minute duration as determined by the Investigator.

Exclusion Criteria	
In addition, any Study Participant that meets the following criteria will be excluded from study enrollment.
 
1.0 Participant unable or unwilling to provide informed consent.
 
2.0 Has a known history of neurologic (excluding stroke) injury.
 
3.0 Has severe aphasia and/or a speech/language disorder, limiting ability to express needs and comprehend instructions.
 
4.0 Has an external lower limb prosthetic ("artificial limb").
 
5.0 Has a hearing impairment.
 
6.0 Had orthopedic surgery in the last year.
 
7.0 Has co-morbidities that prevent participation in exercise (for example: musculoskeletal, cardiovascular, pulmonary and neurological – other than stroke).
 
8.0 Vulnerable populations as deemed inappropriate for study by site Principal Investigator.

Procedures	
ARM A: STANDARD OF CARE + MR-STRIDE PLUS
 
For Study Participants randomized into Arm A, therapy sessions will begin within twenty-four (24) hours of enrollment. Intervention Phase 1 of the study requires a minimum of one (1) therapy session with the possibility of additional sessions until discharge; however, no more than 3 therapy sessions should occur during a given week. Intervention Phase 2 of the study requires 3 independent, remote therapy sessions a week regardless of discharge setting (e.g., rehabilitation hospital or home). Therapy will continue until day 90 (+/-7) following discharge from acute care. Therapy sessions with the MR-Stride Plus should not replace standard of care physical therapy, but be used in addition to standard of care physical therapy.
 
Participants may be contacted by the study staff to collect data on the number of standard of care physical therapy services provided and occurrence of readmission to acute care.
 
Participants will be able to schedule their three (3) sessions a week therapy according to their needs. Participants will be allowed to miss sessions if they are unable to make them up on a different day in the week. Participants therapy activity will be monitored remotely by the study team. If participants are unable to maintain the therapy schedule, the study will contact the participants to gauge willingness to continue. At investigator discretion and participant agreement, the number of sessions a week may be reduced or the participant may withdraw from therapy. If the participant is withdrawn from therapy, participants will be asked if they are willing to participate in a gait speed assessment using the MR-Stride Plus at day 45 and 90 post-discharge if they have not already been completed.
 
The 6-meter walk test (approximately 20 feet) will be conducted to evaluate gait speed at screening and biweekly thereafter until study completion. Gait speed will also be assessed at

	
the time of withdrawal from study therapy if withdrawal occurs before Day 90 (+/-7) post discharge.
 
At the initial therapy session, Study Participants will be provided with all necessary equipment (pre set-up) and instruction for using the MR-Stride Plus. Study staff will provide appropriate oversight of the Participant during their initial walking therapy session in acute care to ensure safety; study staff will not be required to provide any instruction on use of the device. Participants will conduct 30 minutes of walking therapy at the participant's self-selected pace in a space (e.g., track or hallway) that limits the amount of stops and/or pivot turns in order to optimize velocity. Participants may choose to take breaks as needed, or when investigators believe that a rest break is necessary. The use of an overhead harness system is prohibited in this study. If technical or medical issues arise, the training session should be terminated to allow for adequate resolution.
 
For independent, remote therapy sessions following discharge from the acute care hospital, it is not required that a participant be under the supervision of clinical staff or a caregiver (depending on discharge setting), but participants may choose to according to their preference. Participants should perform their therapy sessions in an environment that limits safety hazards and, in a space, e.g., track or hallway, that limits the amount of stops and/or pivot turns in order to optimize velocity. Participants will perform their 30 minutes of walking therapy at their self-selected pace.
 
MR-Stride Plus Procedure: Study staff and participants will be required to follow the Instructions For Use (IFU) provided by MedRhythms. The IFU will detail all procedures required for proper operation of the system. Study Participants will be trained in utilizing the Stride Plus by the study staff. Mobile devices that have the MedRhythms Stride Plus application installed will be provided for use during therapy sessions. Participants will be provided with a pre-established username and password. No personally identifiable patient information will be recorded or stored in the Stride Plus application.
 
ARM B: STANDARD OF CARE
 
For Study Participants randomized into Arm B, clinical standard of care will be followed with no intervention provided using the MR-Stride Plus. Participants will also complete the 6MWT at screening, baseline and biweekly post-discharge from acute care and at days 45 and 90 (+/-7 days) following discharge.
 
All participants will be followed for 90 days following discharge from acute care facility for initial stroke event and discharge date, discharge setting, number of physical therapy services and occurrence of readmission to acute care will be collected.

Minimizing Bias	The study is not blinded because the primary outcome measure of gait speed renders the likelihood of a placebo benefit unlikely. However, Study Participants will be blinded to the results of the 6-meter walk test (approximately 20 feet). No results will be provided to the Study Participant at any time during participation in the trial.
Study Visits	All key assessments will be conducted at the study site and remotely via telecommunication, as applicable.
Study Duration	Each Participant is required to complete a screening visit. For Participants who are randomized into Arm A (MR-Stride Plus Intervention), therapy sessions will take approximately forty-five (45) minutes for set-up and therapy. After the first therapy session in

	
the acute care setting, participants should be able to complete the setup and therapy session with the MR-Stride Plus independently. Collection of data related to study adherence (for participants in the MR-Stride Plus Intervention), gait speed assessment, standard of care administration, discharge and readmission will be performed by study staff remotely through review of medical records, MR-Stride Plus database, and by contacting the participant over the phone. Once participants have reached 90 days following discharge from the acute care facility for the initial stroke event, no follow-up or subsequent Participant involvement is required.

Study Discontinuation, Drop Out, Withdrawal and Replacement	
Participants may discontinue their participation in the study at any time. A Participant may be withdrawn from the study at any time at the discretion of the Investigator.
 
Participants who are withdrawn or drop out prior to the study endpoint will still have data that was collected up until the withdrawal/drop out eligible for analysis. These Participants will be analyzed in an Intent-To-Treat analysis.

Benefits / Risks	
Benefits
 
This project will facilitate the development and clinical translation of targeted gait interventions that can improve walking ability, including the development of new technology that extends the abilities of clinicians.
 
Risks
 
There are some risks to participating in this study. We have categorized them below as Possible, Less Likely, and Rare risks. In summary, the expected risks include:
 
Possible risks:
 
 • Fatigue • Nausea • Shortness of breath • Muscle or joint soreness • Minor muscle cramps • Loss of balance or fall 
Fatigue; Muscle or joint soreness – Depending on participants' level of disability, sessions will be mildly to moderately strenuous. The participant may become fatigued, or experience joint soreness in their hip, knee, ankle or foot.
 
Fatigue; Nausea; Shortness of breath; Muscle cramps or muscle soreness – As with any exercise, there is the possibility that abnormal responses could occur. These include nausea, shortness of breath, fatigue, muscle cramps or soreness (lasting into subsequent days after testing).
 
Loss of balance or fall:
 
There is a risk of falling to the ground. Participants who typically wear an ankle brace may be asked to walk without the brace. When walking without the brace, the foot and ankle may not be as stable and there is an increased risk of ankle sprains during walking and falling.
 
Less Likely Risks:
 
 • Muscle strain/tear • Injury due to fall (ankle sprain, twisted knee, etc.) • Abnormal physiological response to physical activity • Irregular heart rate • Fainting • Bruising and bleeding

	
Muscle strain/tear; Injury due to fall : Injuries such as muscle strains and tears are also possible due to exercise activities. Injuries due to falling are also possible.
 
Abnormal physiological response; Irregular heart rate; Fainting: As with any exercise, there is the possibility that abnormal responses could occur. These abnormal responses include unexpected changes in blood pressure, irregular heart rate, fainting, or joint injury. This risk is increased in the post stroke population.
 
Bruising and bleeding : Participants who are taking anticoagulants may be at increased risk for bruising and bleeding due to a fall.
 
Rare Risks:
 
 • Heart problems • Hospitalization • Anxiety • Heart attack • Stroke • Death 
Heart and lung problems; Hospitalization: As with any exercise, there is the possibility that abnormal responses could occur. Rare risks associated with exercise could include heart problems or hospitalization and in very rare cases, stroke and death. There is also a risk of pulmonary embolism.
 
Anxiety : There also is a potential risk for Study Participants to become anxious.
 
Many of the investigators are licensed physical therapists and most study staff and students have training in CPR and first aid. All of the aforementioned risks will also be mitigated through the following:
 
 • Potential Study Participants will be provided with the consent form and be provided ample time to read it and ask questions. The research team will address any concerns. Study Participants will be told that participation in the study is completely voluntary and they have the right to withdraw from the study at any time. • Adequate rest periods and water will be encouraged to optimize comfort and reduce fatigue. • Total walking time per therapy session will be limited to one half hour. • Trained investigators may monitor vital signs and check for symptoms of distress during the initial therapy session with the MR-Stride Plus. Any findings out of the ordinary will be reported to the participant's primary healthcare provider or emergency services should they require medical attention. 
All participants are free to end testing or procedures that cause anxiety or discomfort at any time, this will not affect any remuneration or transportation they are entitled to.

Data Analysis	UMass Memorial Health Care will be responsible for data analysis. Intent to treat: All Study Participants that enrolled in the study, regardless of withdrawal or incomplete data (if analysis can be made)

Confidentiality	
The Principal Investigator and designees, employees, and agents involved with this study will comply with relevant state and federal laws relating to the confidentiality, privacy and security of Participant's health information. They will only create, maintain, use or disclose any data that is generated by this study or other information disclosed to the Principal Investigator or their employees or agents during the course of the study to MedRhythms, Institutional Review Board, Regulatory Authority or other authorized recipients as appropriate for the execution, analysis, review and reporting of this study. Such information shall not be used for any other purposes and will remain confidential.
 
Study Participants will be informed that all data collected for study purposes will be held in strict confidence and used for research purposes only. Records may be paper or electronic. Privacy of participants will be protected by conducting all in-person interactions in a semi-private or private space within the rehabilitation laboratories. No personally identifiable information will be discussed in common areas.
 
Paper Documents
 
Will be stored in a locked file cabinet that only the study staff has access to. Study Participant files may also be scanned and stored on a secure, password-protected server authorized to store restricted data, with access provided only to the PI and key study staff.
 
Codified Study Participant Identification Number
 
Data collected during this research will be labeled using a codified participant identification number.
 
Research Data
 
Data collected specifically for the study will be labeled with the applicable Study Participant ID and stored on a secure, password-protected server. Data may be transferred as a local copy to password-protected study staff computers for processing or to prepare media material for publications, presentations or training purposes.
 
System Data
 
The MR-Stride Plus device will collect and store data related to the platform's performance on a secured cloud-based drive owned by MedRhythm's. Personally identifiable information will not be collected by the platform or stored by the company. Only the PI and designated study staff will have access to the data collected under this protocol. The PI and all study staff will have access to all coded data housed on a password-protected secured network drive.

Compliance	
Changes or amendments to the protocol will be submitted to the institutional review board (IRB), as required. Subsequently, Study Participants will be notified of protocol changes that may affect their participation in the study. Further participation may be contingent upon re-signing an Informed Consent form.
 
Protocol deviations will be collected and described in the final report.
 
Occurrences of adverse events will be described and recorded and any medical attention sought will be documented. If a deviation in data collection/usage, adverse or unanticipated event involving risks to participants or others, or a breach in confidentiality is suspected or found, the study will be halted until a resolution is determined in accordance with the Institutional Review Board.

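### Is simple randomization a flaw in an open trial of about 40, where blocks stratified by screening gait speed could have been used?

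*Protocol*

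**What the plan says.** The Protocol's Study Design section plans a single-site trial of about 40 people, "randomized using simple randomization into one of two arms. It is expected that study participants will be approximately equally distributed to either arm (20/20". It names no blocks and no strata. The same section says: "A member of the study team will seek informed consent and review inclusion and exclusion criteria to determine eligibility".

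The first item under Primary Endpoint is "Change in gait speed (m/s) from baseline to study completion". Inclusion criterion 4.0 requires a participant to be "Currently able to walk at a speed greater or equal to 0.4m/s, but less than 1.0m/s", so a gait speed is on record before allocation.

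Several entry criteria call for judgement: inclusion 5.0 ("Demonstrates some level of asymmetry in gait"), inclusion 9.0 ("Able to safely participate in protocol-defined walking therapy sessions of 30-minute duration as determined by the Investigator") and exclusion 8.0 ("Vulnerable populations as deemed inappropriate for study by site Principal Investigator"). Minimizing Bias states that the study is not blinded. The Protocol gives no significance level, power, effect size or standard deviation, so the allocation method cannot miss a stated target.

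**The concern.** With about 40 participants, simple randomization often gives visibly unequal arms, and it does nothing to balance the obvious prognostic variable. That variable is already measured for eligibility and is of the same kind as the first primary endpoint. With one site, no site stratum is needed, so two strata would be workable.

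Two things are at stake: some precision on average, and protection of a single small trial against an unlucky draw. An analysis plan could adjust for baseline, but it could not undo the allocation.

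**Working it through.** **Inputs.** From the Protocol: n about 40, 1:1, one site, open, screening speed from 0.4 to below 1.0 m/s. Assumed: baseline speed uniform on that range, a stratum cut at its midpoint of 0.7 m/s, blocks of 4 and 6, and all 40 contributing data.

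**1. The plan's own figure.** Under Binomial(40, 0.5) the mean is 20 per arm with SD √(40 × 0.25) = 3.16. The stated expectation of about 20/20 is therefore correct. Exactly 20/20 occurs in 12.5% of trials, 18/22 or closer in 57.0%, 16/24 or worse in 26.8%, and 14/26 or worse in 8.1%.

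**2. Cost of an uneven split.** Relative efficiency is 4k(40 − k)/1600: 0.96 at 16/24 and 0.91 at 14/26. Its average is 1 − 1/40 = 0.975, a loss of about one participant in 40.

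**3. Cost after baseline adjustment.** The variance of the treatment contrast, in units of the residual variance, is 1/(Stt − Stx²/Sxx). Here t is the arm indicator, x is baseline speed, and S denotes centred sums of squares and products. A perfectly balanced 20/20 trial gives 0.1000. Simulation (20,000 trials per design) gives:

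| Design | Mean | 95th percentile | 99th percentile |
|---|---|---|---|
| Simple | 0.1055 | 0.1173 | 0.1277 |
| Blocks, no strata | 0.1028 | 0.1104 | 0.1191 |
| Blocks in two strata | 0.1009 | 0.1031 | 0.1054 |

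- Average: 0.1055/0.1009 = 1.046, square root about 1.0225, so about 2% in standard error.
- Power: if the stratified design has 80% (noncentrality 2.80, two-sided 5%), simple randomization has Φ(2.80/1.0225 − 1.96) = 78.2%.
- Tail: at the 99th percentile, 0.1277/0.1054 = 1.21, or 10% in standard error.
- Other assumed baseline distributions give an average variance gain of 3-5%.

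**4. Cost of the alternative.** Someone who tracks earlier allocations within each stratum and guesses the arm that is behind is right about 68% of the time with blocks of 4 and 6, and 66% with 6 and 8. Under simple randomization the rate is 50%. If acting on the guess shifts each participant's expected outcome by δ towards the guessed arm, the contrast is biased by 2δ(2p − 1), where p is the correct-guess rate. With δ = 0.02 m/s (assumed), this is 2 × 0.02 × (2 × 0.68 − 1) = 0.0144 m/s.

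**5. Gain and cost on one scale.** The variance saved is (0.1055 − 0.1009)s² = 0.0046s², with s the residual SD. The squared bias is 0.0144² = 0.000207. They are equal at s = 0.0144/√0.0046 = 0.21 m/s. The Protocol gives no s, so a range is shown. The ratio of mean squared error, stratified blocks to simple, is (0.1009s² + 0.000207)/(0.1055s²):

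| Assumed s (m/s) | Ratio |
|---|---|
| 0.10 | 1.15 |
| 0.15 | 1.04 |
| 0.20 | 1.006 |
| 0.25 | 0.99 |

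With δ = 0.01 the bias is 0.0072 and break-even falls to 0.0072/√0.0046 = 0.11 m/s. With no steering at all, blocks are ahead at every s. Which design wins therefore depends on quantities that the Protocol does not give.

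**The case for a change.** The best case for changing the method is that a small trial gets one draw. Where a balanced trial would have 80% power, the 5th percentile of draws has 73.5% under simple randomization and 78.8% under stratified blocks. A 16/24 split could not occur with two strata of blocks of 4 and 6: an unfinished block leaves the arms of a stratum at most 3 apart, so 17/23 is the worst case. A between-arm difference in screening speed of 0.05 m/s or more falls from 37% of trials to 9%. The change costs little before enrolment, and predictability can be limited by undisclosed, varying block sizes and by releasing assignments only after eligibility is final.

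The arithmetic stands, and a sponsor confident in its concealment could reasonably choose blocks. Three things keep it from showing a defect.

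- The 37% against 9% is a raw imbalance at an illustrative threshold. Baseline adjustment, which an analysis plan not at hand may specify, removes its expected effect on the contrast. What remains is the variance gain above.
- The two risks differ in kind. A poor draw leaves the estimate unbiased and shows as a wider confidence interval. Selection bias does not show there, and analysis cannot reliably repair it. The safeguards limit it without removing it.
- The gain is calculated only for the first primary objective. Adherence to the device schedule can be measured only in Arm A, so balance between arms does nothing for it. Time to functional change was not modelled.

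Two neighbouring matters do not support the case for blocks. Releasing assignments after eligibility is locked works equally well with simple randomization. Whether the baseline walk is the screening walk (Study Design and the two arms' Procedures word this differently) is a separate question of wording.

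**Conclusion.** The concern does not hold. The Protocol names a valid method and states its expectation correctly, and no power or precision target is missed. The alternative would bring about 2% in standard error and 1-2 points of power on average, with more in the unlucky tail. It would also raise the correct-guess rate from 50% to about 68% in an open, single-site trial whose own team judges eligibility. Keeping allocation unpredictable is a sound reason to stay with simple randomization.

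The size of the gain rests on the assumed baseline distribution and on complete data. The comparison with bias rests on the assumed 0.02 m/s shift and on a residual SD that the Protocol does not state. Neither assumption is needed for the main conclusion: this is a choice between two defensible designs, and nothing in the text needs correcting.

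### Gait speed for primary endpoints 1 and 2 is assessed differently by arm, and the stated data sources do not match the walks assigned after discharge

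*Protocol*

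**What the plan says.** The Primary Endpoint section lists change in gait speed (m/s) from baseline to study completion and time to functional change in gait speed. It names no instrument for either.

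For Arm A, Study Design adds device tests: "Participants will complete a walking test using the Stride Plus at discontinuation to determine the walking speed", and then "At Day 90 (+7 days), participants will complete a walking test using the Stride Plus to determine walking speed". Procedures (Arm A) assigns the 6-meter walk at screening and biweekly from then to study completion. It also offers participants withdrawn from therapy a Stride Plus gait assessment at Days 45 and 90, if they are willing.

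For Arm B, Study Design says "Participants will complete a 6-meter walk test (approximately 20 feet) to measure gait speed at baseline, biweekly post- discharge from acute care", continuing to Day 90. Procedures (Arm B) lists screening, baseline, biweekly after discharge, and Days 45 and 90, calling the test 6MWT. I read that as the 6-meter walk.

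On collection, Study Design says "Participants will not be required to physically visit the study facility for study-specific procedures once they have been discharged from the acute care setting" and "Data required to evaluate the study objectives will be collected from record review and participant interviews". Study Duration says that data including gait speed "will be performed by study staff remotely through review of medical records, MR-Stride Plus database, and by contacting the participant over the phone". Study Visits allows key assessments at the site or remotely, as applicable.

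Minimizing Bias states that the trial is not blinded, and adds: "However, Study Participants will be blinded to the results of the 6-meter walk test (approximately 20 feet").

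**The concern.** A between-arm comparison of gait speed needs the same test, at the same times, obtained in the same way. Here Arm A has two kinds of speed measurement and Arm B has one, and no rule says which Arm A value counts. Site staff who follow Study Design alone would measure Arm A with the device and Arm B with a 6-meter walk at Day 90.

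Two further problems bear on the same endpoints. The serial walks behind endpoint 2 start from different points in the two arms. And the listed data sources do not say how a physical, timed walk is obtained once the participant has left the hospital, which affects both arms.

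At stake is whether a difference between arms reflects walking or measurement, in an open-label trial of about 40 people. An analysis plan could name the value to be analysed, but it cannot recover walks that were not done.

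**Working it through.** The protocol gives no figure to reproduce here, so the main check sets the sections side by side.

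| Item | Arm A | Arm B |
|---|---|---|
| Screening/baseline | 6-meter walk at screening (Procedures) | 6-meter walk at screening and at baseline (Procedures) |
| Serial walks | Biweekly, counted from screening (Procedures) | Biweekly, counted from discharge (Study Design, Procedures) |
| Day 45 | Stride Plus, only after withdrawal from therapy and if willing (Procedures) | 6-meter walk (Procedures) |
| Day 90 | Stride Plus, window +7 days (Study Design) | 6-meter walk, window +/-7 days (Study Design, Procedures) |
| Discontinuation of device | Stride Plus (Study Design) | Not applicable |

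**Instrument.** Two places point to the 6-meter walk: Procedures runs it in Arm A to study completion, which is also where endpoint 1 ends, and Minimizing Bias mentions it directly after naming gait speed as the primary outcome. Neither says that it supplies the endpoint. Every Arm A speed test tied by name to Day 45 or Day 90 uses the device.

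**Sources.** An interview or telephone call does not by itself time a walk. A medical record holds one only if a clinician performed it, and Inclusion Criterion 6 secures a commitment to only one therapy session. The device database cannot serve Arm B, which has no device test. So the listed sources do not by themselves produce the walks that are assigned.

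**Offset.** Let d be the mean device-minus-walk difference and f the share of Arm A whose final value comes from the device.
- Arm A mean change = true change + f x d
- Arm B mean change = true change
- Expected between-arm difference = true effect + f x d

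With f = 1, d enters one for one. With f = 0 there is no instrument bias.

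**Illustration only.** The offset, the SD of change, the 5% level and the t-test are my assumptions. Take 20 per arm, no true effect, f = 1, and SE = SD x sqrt(2/20), which is 0.047, 0.063 and 0.079 m/s for SD 0.15, 0.20 and 0.25. The two-sided rejection rate from the noncentral t with 38 df is:

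| d (m/s) | SD 0.15 | SD 0.20 | SD 0.25 |
|---|---|---|---|
| 0 | 5% | 5% | 5% |
| 0.02 | 7.0% | 6.1% | 5.7% |
| 0.05 | 17.7% | 12.0% | 9.5% |
| 0.10 | 53.8% | 33.8% | 23.4% |

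**Serial schedule.** Read *biweekly* as every two weeks, and let L be the days from screening to discharge. Arm A walks fall on day 14k and Arm B walks on day L + 14k (k = 1, 2, ...). If L is assumed to be 3 to 7, the first serial walk is day 14 in Arm A and day 17 to 21 in Arm B. With time counted from screening, a change in the first 14 days is first seen L days later in Arm B. For later changes the two grids have the same spacing, so neither arm is favoured on average if changes are spread evenly within an interval.

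**Walk count.** Every two weeks gives 90/14 = 6.4, so 6 walks per participant and 6 x 40 = 240 in all. Twice a week gives 90/7 x 2 = 25.7, so about 25 x 40 = 1,000. The word *biweekly* allows either reading.

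**The case against.** The strongest reply is that the 6-meter walk is the only measure assigned to both arms. It runs in Arm A to study completion and is the test whose results are withheld from participants. The Stride Plus tests would then be extra Arm A data, and the choice between two collected values could sit in an analysis plan. Much of this stands: a reader might infer that Arm A's endpoint is meant to come from the device, and the text does not support that. It also does not settle the matter, because the endpoint has no named instrument and Arm A's fixed-day tests are device tests.

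Other strong readings also fail:
- **Cued against uncued walking.** The device is described as one where "This technology uses embedded audio cues to facilitate improvements in walking speed based on Rhythmic Auditory Stimulation", so a reader might infer that its walking test is cued. The protocol does not say so. It leaves operation to instructions for use that are not shown.
- **Post-discharge walks ruled out.** Visits are not required, but they are not forbidden. Study Visits allows site assessment, and Inclusion Criterion 7 allows contact with the treating clinician. The walks are unsecured, not impossible.
- **Gait speed at withdrawal has no instrument.** In Procedures (Arm A) that sentence directly follows the 6-meter walk and most naturally continues it. Only the Study Design device test at discontinuation leaves doubt.

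It is also fair to say that the difference in starting points is small. It is shorter than one 14-day step under the assumed stay, and it matters mainly for early changes.

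**Conclusion.** The point holds: as written, gait speed for endpoints 1 and 2 is assessed with different tests, starting points and Day 90 windows by arm, and the data-source statements do not match the physical walks assigned after discharge. This should be fixed before the primary comparison relies on it.

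The bias is conditional. It arises only if device values supply some Arm A endpoint values, and it then equals f x d. The protocol gives neither f nor d, so the size cannot be computed. The rejection rates above show sensitivity under assumed values and are not a forecast. If the 6-meter walk is done and used in both arms, the instrument bias disappears. What then remains is the difference in schedule and the unsecured collection route, which risks missing or unstandardised values in both arms.

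**What to change.** Reconcile Study Design, Procedures (both arms), Study Visits and Study Duration as follows.

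- State that endpoints 1 and 2 use only the 6-meter walk in both arms, at comfortable pace and averaged over three trials as in Inclusion Criterion 4. Replace 6MWT with that name.
- Give the serial walks one starting point and one defined interval in place of *biweekly*. Keep them, because endpoint 2 needs them.
- Give both arms the same Day 45 and Day 90 walks with the same windows, including Arm A participants withdrawn from therapy.
- State that Stride Plus speeds are descriptive Arm A data and do not enter the between-arm comparison.
- Amend the data-source statements to name one route, the same in both arms, by which the assigned walks are performed and recorded.

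The main cost is a protocol amendment. Naming Day 45 and Day 90 walks for Arm A adds at most 2 x 20 = 40 walks, fewer where they coincide with serial walks. The serial walks themselves are already assigned, but securing them may need staff time, which depends on the interval chosen. Device speeds could no longer stand in for missed walks, so some Arm A values may be missing.
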